10.0 Study Design / Methods

Figure 1 below illustrates the study design.

Telehealth: Participants in this research study may choose to complete the assessment appointment via home-based telehealth (HBT) care (i.e., service delivery to patients in their homes using consumer-friendly, video-conferencing technology) which may likely enhance retention by directly circumventing financial and transportation barriers associated with traveling to MUSC/VA for an in-person session. HBT sessions will be delivered via standard desk, laptop

computer, tablet, or smartphone running MUSC/VA approved applications. Participants who choose telehealth will be required to have their own computer, tablet, or smartphone; however, webcams will be provided to participants for these visits as needed. Participants will be mailed required materials such as alcohol saliva test strips and pregnancy tests. Separate appointments will be made with each partner for instances where study team needs to meet with each individual separately or privately.

Biological samples will not be collected for individuals participating in HBT care, however prior to the assessment appointment the study team will mail pregnancy tests and alcohol saliva strips to test for pregnancy and recent alcohol use. The alcohol saliva strip must read white (indicative of 0.00 BAC to validate the consent and prior to completing any study procedures. Further, prior to proceeding, females will be asked to take a pregnancy test and must provide verbal confirmation of a negative pregnancy test prior to proceeding with the assessment appointment.

Female participants who complete the assessment appointment via telehealth will be required to take an at-home urine pregnancy test during that visit (provided by study team) and confirm a negative result (verbally and with photo of dipstick). The pregnancy tests used in this study are designed for at-home use, come with clear and simple instructions. In very rare and highly unlikely circumstances where the participant is unfamiliar with how to provide a urine sample or take an at-home pregnancy test, study staff can provide further instructions on how to provide a urine sample, how use the dipstick to test, and to differentiate between a positive and negative result. Ability and willingness to perform an at-home pregnancy test is required for telehealth female participants.

Required study supplies for telehealth participants will be shipped overnight via trackable UPS.

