Assessment Procedures. Following informed consent, eligible participants will complete a breathalyzer or saliva alcohol test, urine drug screen, blood draw, and pregnancy test (for women). Participants will have the option to participate in genomic research by providing an extra 7 milliliters of blood during the study blood draw. Participants will complete a psychosocial and medical history assessment (see Table 2). Note that for telehealth participants, biological specimens will not be collected, however, female participants will be required to take a pregnancy test (provided by study staff) and will be required to verbally confirm a negative result prior to continuing with any procedures. Provided that all inclusion and exclusion criteria are met, participants will be scheduled to complete the laboratory testing portion of the study.

Participants will be instructed to abstain from caffeine, nicotine, alcohol or other substances of abuse prior to the laboratory testing procedure. Smokers will be asked to abstain from smoking during study procedures and offered a nicotine patch prior to participation. Nicotine patch dosage will be determined by the number of cigarettes participants smoke daily (≥ 20 cigarettes/day=21mg; 10–19 cigarettes/day = 14 mg patch; 5–9 cigarettes/day = 7 mg patch).

Human Laboratory Procedure. Participants will complete an alcohol cue reactivity task and the TAP procedure approximately 45 minutes after receiving a 40 IU intranasal dose of oxytocin or placebo (i.e., saline). In a recent review of oxytocin studies, 40 IU is within the normal dosing range for humans and is one of the most common single dose concentrations utilized in human research⁷⁸. This literature indicates that a 40 IU dose is safe and effective in eliciting effects on HPA axis reactivity among participants with AUD^{78,79}.

Alcohol Cue Procedure. Consistent with the procedure developed by Monti and colleagues⁸¹, participants will spend 3 minutes holding and smelling a control beverage (water), and reactivity (e.g., craving, urge to use) will be assessed. Following a 3-minute rest period, participants' preferred alcoholic beverage will be presented and poured into an appropriate glass

and they will spend 3 minutes holding and smelling the beverage. Subjective and physiological reactivity will be measured again.

TABLE 2. ASSESSMENT MEASURES

Construct	Measure

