Participants will be screened for acute alcohol withdrawal at the outset of the study. Participants reporting CIWA-Ar scores ≥ 8 will be excluded from participation and referred clinically. All possible efforts to minimize participant burden and distress will be made. All possible efforts will be made to protect the confidentiality of participants' data, except in the event of imminent risk to self or others, or in the event of disclosure of child or elder abuse. In the event that confidentiality must be broken to protect the safety of participants or others, only the data essential to make an adequate report to authorities will be disclosed. All participants will review the IRB-approved informed consent document with research staff in a private room separate from their partner. Through this process, research staff will inform all research participants of the risks of participation, including emotional distress. In the event that a participant experiences substantial distress or reports risk of harm to oneself or others, they will be asked to complete a safety plan. The Mobile Crisis Unit of Charleston County and urgent care services on the MUSC campus and at the Charleston VAMC are additional resources available to study staff and research participants. [name] and her mentor ([name]) are licensed clinical psychologists equipped to help participants manage distress and to evaluate conditions in which participants need additional assistance. In the event that a participant becomes distressed during or following an assessment, I will contact the participant later that day to check-in and the following day to ensure they have received necessary resources, and to assess their safety and welfare. In the event that any serious adverse event occurs resulting from study participation, that event will be reported in writing to the MUSC IRB and NIH within 24 hours. In similar past and ongoing studies, these resources have been sufficient to manage problems or distress related to participation.

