The laboratory procedure may induce some psychological or physical discomfort. However, it is unlikely that participants will incur any additional risk above that experienced in their daily lives. Prior to the aggression testing, participants will be told that if they feel that the TAP shocks are too high, they can either ask the PI to reduce the intensity (through an intercom) or quit the study at no penalty and receive partial payment. [name] (consultant) and colleagues surveyed over 400 men immediately after completing the TAP and one week later. He found that an extremely small proportion (1.8%) of participants reported an increased likelihood of behaving aggressively as a result of participation. These participants denied any specific plans of action and reported one-week later that these feelings did not persist. No participant or partner reported that involvement in the research led to any increased tendencies towards aggression, and no adverse events were reported. Because interview and self-report assessment measures cover topics of a sensitive nature, participants will have the option to decline answering any questions they prefer not to answer. Participants will be informed during the informed consent procedure that no third party, including their partner, will have access to assessment responses with the standard exceptions in the event of suspected or reported child or elder abuse, or risk of harm to self or others. All couples will be debriefed by the study team following the experimental procedure including full disclosure of the study's purposes and procedures. [name] will follow up with any distressed participants later that day via phone and will provide clinical referrals as necessary.

Participants will be informed about the potential side effects of intranasal oxytocin and will be closely monitored by the research team. Oxytocin administration will occur in a fully-staffed clinical environment equipped with ready access to clinicians and emergency care if necessary.

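### For participants assessed before the dosing day, the visible text requires no repeat pregnancy, withdrawal or alcohol check before the dose

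*Combined protocol and SAP*

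**What the plan says.** Section 5.0 excludes pregnant or breastfeeding women, criterion (a), and anyone in acute alcohol withdrawal, defined as a CIWA-Ar score of 8 or more, criterion (g). Section 13.0, item (5), bases the pregnancy exclusion on what the study drug is known to do.

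The checks behind these criteria are placed early. Under Section 10.0, an in-person participant has the alcohol and pregnancy tests after consent, as part of the assessment. A participant "may choose to complete the assessment appointment via home-based telehealth (HBT) care"; in that case a woman "must provide verbal confirmation of a negative pregnancy test prior to proceeding with the assessment appointment", and for alcohol, "The alcohol saliva strip must read white (indicative of 0.00 BAC to validate the consent and prior to completing any study procedures". For withdrawal, Section 15.0 says: "Participants will be screened for acute alcohol withdrawal at the outset of the study".

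Once these are passed, Section 10.0 says: "Provided that all inclusion and exclusion criteria are met, participants will be scheduled to complete the laboratory testing portion of the study". The preparation named for that session is an instruction: "Participants will be instructed to abstain from caffeine, nicotine, alcohol or other substances of abuse prior to the laboratory testing procedure". Section 15.0 gives the place of dosing: "Oxytocin administration will occur in a fully-staffed clinical environment equipped with ready access to clinicians and emergency care if necessary".

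**The concern.** Both exclusions describe a state that can change between assessment and dosing. Pregnancy matters because of exposure to the drug, so the status that counts is the one on the dosing day. Section 5.0 lists no contraception requirement, so a pregnancy arising in the interval is not otherwise addressed in the criteria. Withdrawal can also begin after a screen has been passed, in a sample recruited for alcohol use disorder.

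If assessment and dosing fall on different days and nothing is repeated, the plan can be followed to the letter and still dose someone whom Section 5.0 bars. Alcohol differs slightly, because recent drinking is not itself an exclusion in Section 5.0. There the point is that the instruction to abstain before the laboratory session comes with no stated test.

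**Working it through.** The plan states no figure to reproduce here, so the check is a comparison of the texts.

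1. *Are assessment and dosing separate contacts?* For telehealth, yes. Section 10.0 has the assessment at home, and Section 15.0 has dosing in a staffed clinic. Section 7.0 says in general terms that procedures can be done by telehealth, but the detailed telehealth text in Section 10.0 covers the assessment appointment only. For in-person participants it depends on scheduling: Section 10.0 schedules the laboratory portion after eligibility is met and does not say whether that is the same day.

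2. *Is the interval limited?* No maximum interval between assessment and laboratory portion is stated.

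3. *What does each check control?*
   - Pregnancy test: for telehealth, it controls whether the assessment appointment goes ahead; in person, it is one of the assessment procedures.
   - Alcohol test: for telehealth, it validates consent and comes before study procedures begin; in person, it is one of the assessment procedures.
   - CIWA-Ar: a screen at study entry (Section 15.0). Table 2 lists it without a time point, so the table does not settle its timing.

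   The telehealth wording about coming before any procedures is the nearest thing to a wider requirement. In context it describes a check within that session and does not ask for a second one on the laboratory day.

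4. *What does Table 3 require before the dose?* The laboratory portion has 2 pre-dose rows, at Minutes 0 and 5. Each lists the same 4 measures: VAS, heart rate, blood pressure and cortisol. The dose follows at Minute 10. None of the 4 measures is a pregnancy test, a CIWA-Ar score or an alcohol test.

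5. *Count.* Of the 3 checks, the number that the visible text requires to be repeated between assessment and dose is 0.

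The number of participants affected cannot be computed. The documents give neither the share of telehealth or earlier-day assessments nor the usual interval to dosing.

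**The case against.** The strongest reply is that this is only silence in what can be read. Section 10.0 says "Figure 1 below illustrates the study design", and that figure is not visible; it or an operating procedure could include a re-check. This stands as a limit. A reader might infer that the exclusions are not enforced at dosing, or that nobody is re-checked. The documents do not support that: they show only that the visible text does not require a repeat.

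Second, the study may usually be a single visit. Section 13.0, item (9), describes it so, and Table 3 puts the screening and laboratory portions in one timetable. For anyone assessed and dosed on the same day, the assessment tests serve as the pre-dose check and the point does not apply. It cannot be so for a home telehealth assessment.

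Third, the likely harm is limited. Section 15.0 links the noted risks to intravenous rather than intranasal oxytocin and reports more than 200 participants given this dose without an adverse event. Heart rate and blood pressure are taken twice before dosing, the investigator may discontinue a participant (Section 14.0), and the investigator or primary mentor is present or on call at all visits (Section 13.0, item (6)). All of this lowers the severity, but none of it detects an early pregnancy or yields a CIWA-Ar score.

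A reader might also infer that the CIWA-Ar is scored before abstinence begins, so that withdrawal brought on by abstaining would always be missed. The documents do not say when the instruction to abstain is given or how long abstinence lasts, so that order is not established.

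**Conclusion.** The point holds as a modest safety gap. It is certain in scope for home telehealth assessments and possible for in-person participants whose laboratory portion is on a later day. For them the visible text gives no maximum interval and requires 0 of 3 checks to be repeated before the dose. A participant who became pregnant or entered withdrawal in the interval could therefore be dosed under the plan as written, despite criteria (a) and (g) of Section 5.0.

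This rests on two assumptions: that Figure 1 contains no pre-dose check, and that the telehealth option is used. No count of affected participants is claimed, and no size is put on any effect on the trial's results, since the documents do not show how withdrawal or recent drinking would alter the response to oxytocin. The sample size and error rates are not in question.

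**What to change.** Add one row before Minute 0 in the laboratory portion of Table 3, for any participant not assessed that day: a urine pregnancy test (women), the CIWA-Ar, and a breath or saliva alcohol test. State the action for each:

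- Positive pregnancy test: do not dose; exclude under criterion (a).
- CIWA-Ar of 8 or more: do not dose; exclude and refer, as Section 15.0 already provides.
- Alcohol above 0.00: reschedule, applying the standard Section 10.0 already uses at the telehealth assessment.

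The cost is one protocol amendment and a few minutes of tests that the study already uses. Some visits will be rescheduled, and a prepared dose may occasionally be wasted. If the site already makes these checks, the amendment simply records the practice.

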Eligibility	
 •Phone Screen Questionnaire •Demographics •Health History Interview & Concomitant Medications •Breathalyzer and Urine Drug Screen •Pregnancy (women only) •Mini International Neuropsychiatric Interview⁸² •Revised Conflict Tactics Scale; CTS-2⁸³ •Patient Health Questionnaire; PHQ-9⁹⁹
Dyadic Functioning	
 •Dyadic Adjustment Scale; DAS⁸⁷ •Emotional & Physical Infidelity⁸⁸
Substance Use	
 •Revised Clinical Institute Withdrawal Assessment; CIWA-Ar⁸⁹ •Time Line Follow back; TLFB^{90,91} •Alcohol Use Disorders Test;AUDIT⁹² •Drug Abuse Screening Test; DAST⁹³ •Fagerstrom Nicotine Dependence Test⁹⁴ •Marijuana Motives Questionnaire
Mental Health	
 •Traumatic Life Events Questionnaire; TLEQ⁹⁶ •PTSD Check List; PCL-5⁹⁷ •Childhood Trauma Questionnaire; CTQ⁹⁸ •Patient Health Questionnaire; PHQ-9⁹⁹ • Cognitive Emotion Regulation Questionnaire; CERQ-Short¹⁰¹ • Perceived Stress Scale -4; PSS-4¹⁰² • Interpersonal Sensitivity Measure;IPSM¹⁰³Impulsive Behavior Scale; UPPS
Neuroendocrine	
 •Endogenous Oxytocin (blood) Note: Collected unless staff learn of contraindications. •Cortisol (saliva) Note: Collected unless staff learn of contraindications.
Physiological	
 •Heart Rate (HR) •Blood Pressure (BP)
Subjective	•Visual Analogue Scale (VAS)

TAP Procedure. In the couple-specific TAP utilized in [name] (Consultant) is his ongoing NIAAA-sponsored trial, participants engage in a fictitious reaction time competition with their partner. Participants are led to believe that their partner chooses whether or not they receive a shock and its intensity. Participants have the option to administer a shock to their partner and its intensity in response to a "winning" trial. In reality, participants receive electric shocks in response to a "losing" trial at intervals randomly generated by the TAP software¹⁰⁴. IPA is operationalized as the number of shocks administered, intensity of the first "unprovoked" shock, proportion of maximum shocks selected, and average shock intensity. Each participant will receive the same number of shocks. Electric shocks are brief in duration (1 second), range in intensity from 25-250 mV, and are administered to two fingertips of the participant's non-dominant hand. The TAP task entails 30 trials for a total duration of 12-14 minutes.

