At the outset of the TAP procedure, the words "Get Ready" appear on the computer screen in front of the participant. Then the words "Press the Spacebar" appear on the screen. Participants press and hold the space bar until the words "Release the Spacebar" appear on the screen, at which time the participant will release the spacebar as quickly as possible. A "win" is indicated to the participant with the words "You Won. You May Give a Shock" appearing on the screen.

Following a winning trial, participants choose whether or not to shock their opponent and its intensity on a level ranging from 1 (very mild shock, definitely not painful) through 10 (intense shock, definitely painful). A “loss” is indicated with the words “You Lost. You Will Get a Shock” appearing on the screen. The shock intensity received by the participant is randomly selected by the computer software within the calibrated range specified for each participant.

Calibration: The finger stimulator apparatus (Colbourn Instruments, Whitehall, PA) is calibrated for each participant, controlling for individual differences in pain threshold that may influence shock selection. Two electrodes are attached to the participant’s middle and index finger on the non-dominant hand. Each participant is administered 1-second shocks that increase stepwise beginning with the lowest possible intensity. Participants are instructed to inform the researcher when the shocks are first detectable and then again when they experience a shock as painful. During the actual TAP procedure, shock levels range from 1 to 10 and correspond to the participant’s 55% through 100% pain threshold.

TABLE 3. LABORATORY TESTING

Duration	Procedure
Screening portion	
2-2.5 hours	Informed consent and assessment battery
30 minutes	Blood draw from nurse from Research Nexus
Laboratory portion	
Minute 0	Baseline measurement #1 (VAS, HR, BP, cortisol)
Minute 5	Baseline measurement #2 (VAS, HR, BP, cortisol)
Minute 10	Oxytocin or placebo administered
Minute 40	Post-medication assessment (VAS, HR, BP, cortisol)
Minute 45	Alcohol Cue
Minute 50	Post-Cue assessment (VAS, HR, BP, cortisol)
Minute 65	TAP
Minute 70	Immediate post-task assessment (VAS, HR, BP, cortisol)
Minute 85	15-minute post-task assessment (VAS, HR, BP, cortisol)
Minute 100	30-minute post-task assessment (VAS, HR, BP, cortisol)
Minute 130	60-minute post-task assessment (VAS, HR, BP, cortisol)
Minute 135	Participant debriefed, compensated and discharged

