12.0 Data Management and Statistical Analysis Plan

Descriptive statistics will be used to characterize participants at each time point. Because the units of randomizations are dyads (i.e., couples), all analyses will account for potential within-dyad correlation (e.g., intraclass correlation [ICC]). Generalized linear mixed models (GLMMs) with random couple effects will be used to assess group differences in baseline characteristics. These can be operationalized using SAS Proc Mixed and Proc GLIMMIX. Should any variables

exhibit significant departures from normality, variable transformations (e.g., logarithmic) or non-parametric approaches will be used, as appropriate. GLMMs are ideal for handling analyses involving correlated measures¹⁰⁸, and they will allow us to estimate both the between- and within-couple variation. GLMMs are also useful for modeling longitudinal (repeated) outcomes on individual subjects, and the models can be adapted with appropriate link functions for continuous, binary, and count outcomes. GLMMs will be constructed for analyses involving group (or subgroup) comparisons over time. The models will also control for relevant covariates, including baseline outcome levels and number of standard drinks during the 60 days prior to participation. Various covariance structures (e.g., compound symmetry, autoregressive, etc.) will be tested, with final model selection based on fit statistics such as Akaike Information Criterion¹⁰⁹. Analyses will be conducted using SAS v9.4 (Cary, NC).

Hypothesis 1: Participants who receive oxytocin, as compared to placebo, will demonstrate significantly lower craving, aggression, physiological (HR, BP), and neuroendocrine (cortisol) reactivity to the TAP. To test this hypothesis, GLMMs with identity link functions (for continuous measures) and log link functions (for count data) will be used to model the between-group differences. Random couple effects will be used to account for within-couple correlation.

Hypothesis 2: Oxytocin response will be greater among women as compared to men. To test this hypothesis, GLMMs will be used to assess serially measured time points following medication administration (15, 30, and 60 minutes post task). The effects of gender, time, and their interaction will be assessed. Primary outcomes include alcohol craving, aggression, and cortisol.

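### TAP shock strength received is a random draw with no common schedule or named adjustment, which probably adds avoidable noise to the three provoked aggression measures

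*Combined protocol and SAP*

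**What the plan says.** Section 10.0 (TAP Procedure) describes a sham reaction-time contest in which participants think their partner decides whether they are shocked and how hard. In fact the software decides:

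- Strength: "The shock intensity received by the participant is randomly selected by the computer software within the calibrated range specified for each participant".
- Timing: shocks follow losing trials "at intervals randomly generated by the TAP software".
- Count: "Each participant will receive the same number of shocks".
- Scale: "shock levels range from 1 to 10 and correspond to the participant’s 55% through 100% pain threshold".
- Length: "The TAP task entails 30 trials for a total duration of 12-14 minutes". The split between wins and losses is not given.

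Four measures come from the task: "IPA is operationalized as the number of shocks administered, intensity of the first 'unprovoked' shock, proportion of maximum shocks selected, and average shock intensity".

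On adjustment, section 12.0 says: "The models will also control for relevant covariates, including baseline outcome levels and number of standard drinks during the 60 days prior to participation". The level of shock received is not named there. Table 3 schedules the TAP once, at minute 65, after dosing at minute 10.

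Section 15.0 adds that participants who find the shocks too strong "they can either ask the PI to reduce the intensity (through an intercom) or quit the study at no penalty".

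**The concern.** Because participants attribute each shock to the partner, its strength is the provocation they are answering. The plan fixes the number of provocations and scales them to each person's pain threshold. Neither step fixes the level drawn on the 1 to 10 scale. If the draws differ between people, one participant may face a mild apparent partner and another a harsh one, by luck alone.

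The named covariates cannot absorb this, because a software draw is unrelated to drinking history or any other baseline characteristic. No baseline TAP score is scheduled in any case.

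What is at stake is precision on aggression, the outcome used to justify the sample size. The variation would enter the number of shocks given, the proportion at maximum and the average intensity. It is avoidable because the software generates the level itself.

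**Working it through.** **Inputs from the documents.** SD of TAP aggression 1.1, target difference 0.4 units, 100 people (50 couples) per arm, two-sided alpha 0.05 or, for the between-group claim, 0.25 with 80% power (section 12.0); levels 1 to 10, 30 trials (section 10.0).

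**Assumptions, not in the documents.** k = 15 losing trials (10 and 20 also shown); independent uniform draws over levels 1 to 10; a slope b, the change in a participant's mean intensity set per one-level change in mean level received, of 0.2 to 0.5.

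**Step 1: the plan's own power figure.** With independent people, SE = 1.1 × √(2/100) = 0.1556 and 0.4/0.1556 = 2.571.

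- Alpha 0.25: Φ(2.571 − 1.150) = 92.2%.
- Alpha 0.05: Φ(2.571 − 1.960) = 73.0%.

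Allowing for couples, effective n = 100/(1 + ICC). At alpha 0.25, ICC = 1 gives 74.8% and ICC = 0.666 gives 80.0%. The stated 80% is therefore reached only with a within-couple correlation that the plan does not give. That is a separate matter and does not show the figure to be wrong. Two settings are carried forward: A (alpha 0.25, ICC 0.666, power 80.0%) and B (alpha 0.05, ICC 0, power 73.0%).

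**Step 2: spread of provocation.** Variance of one draw = (10² − 1)/12 = 8.25, so the SD is 2.87. The mean of 15 draws has variance 8.25/15 = 0.55 and SD 0.742. About 95% of participants would have a mean received level between 4.1 and 6.9, around 5.5. The SD is 0.91 with 10 losses and 0.64 with 20.

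**Step 3: share of outcome variance.** Share = b² × 0.55 / 1.1².

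- b = 0.2: 0.022/1.21 = 1.8%
- b = 0.3: 0.0495/1.21 = 4.1%
- b = 0.5: 0.1375/1.21 = 11.4%

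Over b = 0.2 to 0.5, the share is 2.7% to 17% with 10 losses and 1.4% to 8.5% with 20.

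**Step 4: power if the noise is removed.** Suppose that the SD of 1.1 already contains the noise and that partners' draws are independent. The variance of the arm difference is then (2/100) × [1.21 × (1 + ICC) − b² × 0.55]. For b = 0.5 in setting B this is 0.02 × 1.0725 = 0.02145, so SE = 0.1465 and power = Φ(2.731 − 1.960) = 78.0%. In setting A it is 0.02 × (2.0159 − 0.1375) = 0.03757, so SE = 0.1938 and power = Φ(2.064 − 1.150) = 81.9%.

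| b | Share of variance | A: from 80.0% to | B: from 73.0% to |
|---|---|---|---|
| 0.2 | 1.8% | 80.3% | 73.7% |
| 0.3 | 4.1% | 80.7% | 74.7% |
| 0.5 | 11.4% | 81.9% | 78.0% |

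If the noise instead comes on top of 1.1, the 80.0% in setting A falls to 79.3% at b = 0.3 and 78.1% at b = 0.5.

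**Step 5: chance difference between arms.** SE of the difference in mean received level = 0.742 × √(2/100) = 0.105, so 95% of trials fall within 1.96 × 0.105 = 0.21 levels. At b = 0.2 to 0.5 that is 0.04 to 0.10 units, against the 0.4-unit target.

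These sums apply to average intensity. The documents give no SD for the other two provoked measures, so the effect on them is not sized.

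**The case against.** The strongest reply is that random provocation is a legitimate design choice. Provocation is already standardised in count and in relation to pain threshold, the covariate list is open-ended, and the SD of 1.1 comes from earlier TAP work and may already include this variation. All of that is fair. It limits the size of the point but does not remove it: the level received is still unscheduled and unnamed, and noise already inside the SD can still be taken out.

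Four stronger readings are tempting, and the documents do not support them.

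- **That every TAP measure is affected.** The first unprovoked shock is, by its name, set before any provocation. Because shock timing is random and the plan does not say that the first trial is a win, this deserves confirmation, but it is no ground for including that measure.
- **That each person certainly gets fresh draws.** In the quoted sentence, the closing words about each participant describe the calibrated range, not the draw. One stored random sequence mapped onto each range would also fit. Fresh draws are only the likelier reading.
- **That the arms are biased.** The draws do not depend on arm. The chance shift in step 5 is the same sampling error as the added variance, already in the standard error, and must not be counted as a second harm.
- **That data after a requested reduction in intensity are pooled without distinction.** Section 15.0 allows the reduction, and the documents are silent on how it is recorded or analysed. Silence does not establish pooling.

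**Conclusion.** The point holds as a modest, optional gain in precision. If draws differ between participants, chance variation in provocation adds noise to the three provoked measures and leaves the oxytocin-placebo comparison unbiased. With 15 losses and uniform draws, it accounts for about 2% to 11% of the variance of average intensity at slopes of 0.2 to 0.5. For slopes of 0.3 to 0.5, removing it is worth about 0.7 to 1.9 power points at alpha 0.25 with ICC 0.666, and 1.7 to 5.0 points at alpha 0.05 with ICC 0. At a slope of 0.2 the gain is under one point in either setting.

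The slope drives the result, and nothing in the documents informs it. The number of losses and the uniform distribution are also assumed. If the software already uses one stored sequence for everyone, the point falls away.

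**What to change.** First, state whether the software draws levels afresh for each participant or uses one stored sequence.

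If it draws afresh and logs the levels, prespecify each participant's mean software-drawn level as a covariate in the models for the three provoked measures. Use the level on the 1 to 10 scale as drawn, not as delivered after any requested reduction, so that the covariate stays independent of treatment. The cost is one extracted variable and one model term.

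For participants not yet run, the alternative is one preset sequence of wins, losses and received levels, mapped to each person's calibrated scale and common to both arms. Fixing wins and losses as well as levels also removes variation in timing. The small cost is that results then apply to one provocation sequence. If the switch is made mid-trial, record the task version and include it in the model.

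The participant's right to ask for a reduction stays as it is. An analysis restricted to trials before a reduction is not recommended, because it selects on an event after randomisation that treatment could influence.
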